#### **9.1.4. Postoperative Care Through 96 Hours (T96h)**

After surgery, subjects will be monitored for 96 hours (through T96h) at the trial site as an inpatient. Safety and efficacy evaluations will be performed and blood drawn for PK assessments (for the PK study). Subjects will be required to meet standard pre-specified criteria for discharge from the unit. Note that topical ice packs or cooling treatments are prohibited during the inpatient period for use on the foot near the surgical site. Such treatments are allowed to treat conditions remote from the surgical site. After discharge, topical ice packs or cooling treatments may be used over the surgical site or elsewhere.

The schedule of assessments are as follows:

- Perform NRS assessments of current pain intensity:
  - During the inpatient stay, at T0.5, 1, 2, 4, 6, 8, 12, 16, 20, 24, and every 4 hours (if awake at time of assessment and if no rescue opioid had been administered in the past 4 hours) until discharge from the inpatient unit.
  - Pain scores may be skipped between the hours of midnight and 6 a.m., but the subject may not miss two consecutive assessments.
  - An additional NRS assessment must be obtained 4 hours ( $\pm 15$  min) after every rescue dose even if this time point occurs between midnight and 6 a.m. The subject must be awakened if asleep to assess this NRS.
  - The T12, T24, T48, T72 and T96h assessments must be completed even if the subject is asleep at these times.
  - During the inpatient stay, starting on postoperative day 1 (after T24): each morning on arising at approximately 0800h ( $\pm 2$ h) and each evening prior to bedtime at approximately 2000h ( $\pm 2$ h) document the NRS score with ambulation (partial or full; must document time of assessment). Actual assessment times must be documented.
  - There will be a  $\pm 5$  minute window allowed for the collection of each assessment in the first 4 hours after the end of surgery, after which will be a  $\pm 15$  minute window allowed.
- Record vital signs: 1, 2, 4, 6, 12, 24 and every 8 hours thereafter (if awake at time of assessment between the hours of 00:00 and 06:00) until discharge from the inpatient unit (may not miss two consecutive assessments). There will be a  $\pm 5$  minute window allowed for the collection of vital signs in the first 4 hours after the end of surgery, after which will be a  $\pm 15$  minute window allowed. Daily temps can be recorded along with vital signs per site SOPs at 1, 2, 4, 6, 12, 24, and every 8 h thereafter until discharge from the inpatient facility (if awake at the time of assessment between hours of midnight and 6 a.m.).
- Perform interim PE: surgical site assessment and neurosensory exam of the foot proximal to the surgical site with contralateral comparison prior to discharge from the inpatient unit.

- Perform ECG: at 24 ( $\pm$ 2) hours after surgery.
- Clinical laboratory tests (chemistry, hematology and urinalysis): at 96 hours prior to discharge from the inpatient unit.
- If the subject is participating in the PK study, obtain whole blood for PK analyses: at baseline (within the 30 min before the start of study treatment dosing), and T5min, T10 min, T15min, T30min, T45min, and T1, T1.5, T2, T2.5, T3, T4, T6, T8, T12, T16, and T24h, for a total of 17 samples).
- Subjects with inadequately controlled pain may request and receive rescue medication at any time; however, subjects will be encouraged to receive rescue only for an NRS  $\geq$  4. Additionally, subjects should be encouraged to wait at least 1 hour after completion of surgery (EOS) before utilizing pain rescue medication, if possible. NRS must be completed within 15 minutes prior to use of pain rescue medication if the time between rescue request and consumption is prolonged.
- Document the time to first use of rescue medication after T0 (between T0 and T24h) and after T24 (between T24h and T96h).
- Document concomitant medication use including doses and times taken
- All AEs that occur from the time a subject's informed consent but prior to study treatment will be captured in the medical history. All AEs and SAEs will be documented and followed from the time of administration of study treatment and will be considered treatment-emergent AEs (TEAEs).

After completing the assessments through T96h hours after study treatment administration and prior to discharge from the inpatient unit, review with the subject the use of a diary for at-home use to record pain assessments and medication use (including pain medication) at home.

Additionally, obtain the subject's global assessment of satisfaction with study treatment (patient global evaluation or PGE) and the investigator's global evaluation (IGE) prior to discharge. Finally, instruct subjects to return to the study center on D8 $\pm$ 1 for a follow-up assessment.

Once discharged from the inpatient unit, all study participants will be instructed to take a combination of OTC analgesics (NSAID and acetaminophen) at an appropriate dose per medical judgment to manage any residual or breakthrough postsurgical pain through D29/W4.

Outpatient period: D4 through D29/W4:

- If needed for pain management, over-the-counter (OTC) analgesics administered PO, e.g.,
  - NSAID (e.g., ibuprofen 200 mg to 400 mg prn qid [Advil® or Motrin®] or naproxen 220 mg prn tid [Aleve®]) or other options per investigator discretion **and**
  - Acetaminophen 1-2 500 mg tablets (up to 1 g) prn tid or 650 mg prn qid (3g daily limit)

- If a subject is still requiring opioid rescue in the 12h prior to discharge (i.e., from T84h on regardless of whether discharge is delayed), prescribe oxycodone 5 mg PO tid prn (medical discretion on dosing and number of tablets dispensed per consideration of subject's age/history and needs, but no more than six tablets should be prescribed and may be taken as needed over the next several days). If additional oxycodone is required, refills are left to investigator discretion.

Persistent pain or pain exacerbations during this period may suggest the need for an unscheduled in-person visit to assess the surgical site. If such a situation occurs, the Investigator should use clinical discretion on adequacy of analgesic treatment, but to capture this event as an adverse event (AE) and document any required treatments.

#### **9.1.5. Outpatient Phase: D8±1 (W1) Visit**

Subjects will return to the study center on D8±1 (W1) for the following assessments:

- Subject home diary review
- Document pain intensity (NRS) at rest and after ambulation (approximately 10 yards) each day since discharge from the inpatient unit
- Record vital signs (HR, BP and RR)
- Perform interim PE: surgical site assessment and neurosensory exam of the foot proximal to the surgical site with contralateral comparison
- Document concomitant medication use including doses and times taken for analgesic medications
- Document concomitant treatment use including topical ice pack or cooling treatments (only allowed during outpatient period)
- Record AE Assessment
- Obtain PGE assessment
- Obtain IGE assessment

In their diary, subjects will assess their current pain intensity at rest and after ambulation each morning (08:00 ±3 hours), and each evening (20:00 ±3 hours) using the NRS. The subject should be instructed to perform, if possible, the daily assessments as follows:

- Obtain the morning NRS assessment prior to taking any pain medication or approximately 2 hours after taking any pain medication
- Obtain the evening NRS assessment approximately 2 hours after taking any pain medication

Subjects should be instructed to record any medication they take (dose and time) whether to treat their pain or for any other reasons.

**9.1.6. Outpatient Phase: D15±2 (W2) Visit**

Subjects will return to the study center on D15±1 (W2) for the following assessments:

- Subject home diary review
- Document pain intensity (NRS) at rest and after ambulation (approximately 10 yards) each day since discharge from the inpatient unit
- Record vital signs (HR, BP and RR)
- Perform interim PE: surgical site assessment and neurosensory exam of the foot proximal to the surgical site with contralateral comparison
- Document concomitant medication use including doses and times taken for analgesic medications
- Document concomitant treatment use including topical ice pack or cooling treatments
- Record AE Assessment
- Obtain PGE assessment
- Obtain IGE assessment

In their diary, subjects will assess their current pain intensity at rest and after ambulation each morning (08:00 ±3 hours), and each evening (20:00 ±3 hours) using the NRS. The subject should be instructed to perform, if possible, the daily assessments as follows:

- Obtain the morning NRS assessment prior to taking any pain medication or approximately 2 hours after taking any pain medication
- Obtain the evening NRS assessment approximately 2 hours after taking any pain medication

Subjects should be instructed to record any medication they take (dose and time) whether to treat their pain or for any other reasons.

**9.1.7. Outpatient Phase: D29±2 (W4) Visit**

Subjects will return to the study center on D29±2 (W4) for the following assessments:

- X-ray of the surgical site
- Record vital signs (HR, BP and RR)
- Perform interim physical exam: surgical site assessment and neurosensory exam of the foot proximal to the surgical site with contralateral comparison
- Document concomitant medication use including doses and times taken for analgesic medications
- Document concomitant treatment use
- Record AE Assessment
- Obtain PGE assessment
- Obtain IGE assessment

- When assessed, if the Investigator observes insufficient wound healing or atypical findings on surgical site assessment or to follow up on any unresolved AE, the subject may be scheduled for a follow-up visit on D36±2. If the wound is considered healed at D29, the D36 visit is not required.)

#### **9.1.8. Outpatient Phase: Optional D36±2 (W5) Visit**

If required due to any ongoing safety issue, insufficient wound healing or atypical findings on surgical site assessment noted at Day 29 visit or to follow up on an unresolved AE, subjects will return to the study center on D36±2 (W5) for the following assessments:

- Record vital signs (HR, BP and RR)
- Interim PE focusing on the surgical site assessment and neurosensory exam of both feet (proximal to the surgical site)
- Concomitant Medication Use including doses and times taken for analgesic medications
- AE Assessment

#### **9.1.9. Early Termination Visit**

If willing, subjects who elect to prematurely discontinue from the study will be requested to come in at their convenience for the following assessments (if subjects are not willing to return for assessments, request that they at least come in to assess the surgical site to ensure adequate wound healing):

- Record vital signs (HR, BP and RR)
- Perform surgical site assessment and neurosensory exam of the foot proximal to the surgical site with contralateral comparison
- Document concomitant medication use including doses and times taken for analgesic medications
- Document concomitant treatment use
- Record AE Assessment

#### **9.1.10. Unscheduled Visits**

Unscheduled visits may be scheduled at any time if warranted due to the subject's complaints or condition per investigator discretion. Assessments performed at Unscheduled Visits will be at the discretion of the investigator. If these visits occur prior to D29±2 (W4), perform the following:

- Record vital signs (HR, BP and RR)
- Interim PE focusing on the surgical site assessment and neurosensory exam of both feet (proximal to the surgical site)
- Concomitant Medication Use including doses and times taken for analgesic medications

- Concomitant Treatments including topical ice pack or cooling treatments
- AE Assessment

## 9.2. Discussion of Study Design

This trial is designed to determine the efficacy of study treatment (CA-008 vs. placebo) infiltrated/instilled during surgery in treating postoperative pain after a bunionectomy in the setting of multimodal analgesia in addition to a Mayo block with bupivacaine in the first 24h and to confirm the safety profile observed in the phase 1 study recently completed. For the PK study, additional assessments will be done to further characterize the PK profiles of CA-008, CA-101 and capsaicin.

The current design, post-operative pain following elective primary unilateral first metatarsal bunionectomy surgery with osteotomy, has been used as a model of postoperative pain previously. In this model, the pain is generated from the correction of hallux valgus deformity of the first metatarsal and is used as a model to evaluate the treatment effect on duration of acute pain (multiple-day efficacy) ([Singla 2013](#); [Wang 2010](#)).

Randomization will be used to avoid bias in the assignment of subjects to treatment, to increase the likelihood that known and unknown subject attributes (e.g., demographics and baseline characteristics) or other variables are evenly balanced across treatment groups, and to enhance the validity of statistical comparisons across treatment groups.

A placebo control will be used to establish the frequency and magnitude of changes in clinical endpoints that may occur in the absence of active treatment as well as to minimize subject and investigator bias. Double-blinded treatments will be used to reduce potential bias of subjects and investigators during data collection and evaluation of clinical endpoints.

## 10. SELECTION OF STUDY POPULATION

### 10.1. Inclusion Criteria

Subjects must meet all of the following criteria to be considered eligible to participate in the study:

1. In the medical judgment of the investigator, be a reasonably healthy adult aged 18 - 75 years old, inclusive, and American Society of Anesthesiology (ASA) physical Class 1, 2 or 3 at the time of randomization ([Appendix 1A](#)).
2. Plan to undergo an elective primary unilateral first metatarsal Bunionectomy repair, without collateral procedure or additional surgeries, to be performed under light to moderate sedation with regional anesthesia.
3. If a male, unless he has a same sex partner, be either sterile (surgically **or** biologically) or commit to an acceptable method of birth control while participating in the study. The site personnel will provide instructions on what is an acceptable method.
4. If a female of child-bearing potential (FCBP), must meet **all** of the following:
  - a. Not be pregnant (FCBP must have a negative serum pregnancy test at screening and negative urine pregnancy test before surgery);
  - b. No plan to become pregnant or to breast feed during the study; and
  - c. Be surgically sterile or at least one year post-menopausal, have a monogamous partner who is surgically sterile, have a same sex partner or (**one** of the following must apply)
    - i. is practicing double-barrier contraception
    - ii. is practicing abstinence (must agree to use double-barrier contraception in the event of sexual activity)
    - iii. is using an insertable, injectable, transdermal or combination oral contraceptive approved by the FDA for at least 2 months prior to screening and commits to the use of an acceptable form of birth control while participating in the study.
5. Have a body mass index  $\leq 40$  kg/m^2.
6. Be willing and able to sign the informed consent form (ICF) approved by an Institutional Review Board (IRB).
7. Be willing and able to complete study procedures and pain scales and to communicate meaningfully in English with study personnel and return for outpatient follow up visits as

required.

8. For the portion of subjects who will participate in the PK analyses, be willing to undergo 17 blood draws for PK assessments at various time points during the surgery and the following 24 hours.

## 10.2. Exclusion Criteria

Subjects will not be eligible to participate in this study if any one of the following exclusion criteria is met:

1. In the opinion of the Investigator,
  - a. have a concurrent painful condition, other than bunion-related pain, that may require analgesic treatment during the study period or may confound post-surgical pain assessments.
  - b. have active skin disease or other clinically significant abnormality at the anticipated site of surgery that could interfere with the planned surgery.
2. Have a known allergy to chili peppers, capsaicin or the components of CA-008, bupivacaine HCl, ketorolac, acetaminophen or oxycodone.
3. As determined by the investigator (with input from the study's medical monitor if requested by the investigator), have a history or clinical manifestation of significant medical, neuropsychiatric or other condition, including a clinically significant abnormal clinical laboratory test value, that could preclude or impair study participation or interfere with study assessments.
4. The following are considered disallowed medications:
  - a. Be tolerant to opioids defined as those who have been receiving or have received chronic opioid therapy greater than 15 mg of oral morphine equivalents ([Table 5](#)) per day for greater than 4 out of 7 days per week over a one-month period within 6 months screening.
  - b. Within 1 day prior to surgery and throughout the inpatient period, be taking any capsaicin-containing products, such as dietary supplements or over-the-counter (OTC) preparations, including topical formulations, and prescription medications.
  - c. Within the 7 days prior to surgery, be taking any central nervous system (CNS) active analgesic adjunct medication, such as anticonvulsants, antidepressants (such as SNRIs, SSRIs, and tricyclic antidepressants), benzodiazepines, sedative-hypnotics, clonidine and other central alpha-2 agents (e.g., tizanidine), ketamine

or muscle relaxants. [Note that SNRIs = Serotonin and norepinephrine reuptake inhibitors and SSRI = Selective serotonin reuptake inhibitors.]

- i. These drugs are permitted if prescribed for non-pain indications and the dose has been stable for at least 30 days prior to surgery. Note that the dose must remain stable throughout the study.
    - ii. If the subject is taking centrally- and/or peripherally-acting analgesic medications, such as acetaminophen, NSAIDs, tramadol or opioids, FOR bunion-related pain, the subject may participate in the study if 4(a) above is not applicable and the subject is willing to discontinue these medications 3 days prior to surgery.
    - iii. The use of benzodiazepines and the non-benzodiazepines (eszopiclone, ramelteon, zaleplon and zolpidem) are permitted to treat insomnia during the postoperative period.
  - d. Within the 7 days prior to the planned surgery and throughout the study, be taking antiarrhythmics except beta-blockers, digoxin, warfarin (see exception below), lithium, or aminoglycosides or other antibiotics for an infection (except for ophthalmic use or for treatment or prophylaxis of postoperative surgical site infections). (Use of warfarin or other agents is allowed, at the investigator's discretion, for DVT prophylaxis after the surgery is completed).
  - e. Within the 14 days prior to surgery, be taking parenteral or oral corticosteroids (steroid inhaler for allergy or asthma treatment, topical steroid for a non-clinically significant skin condition not involving the area of surgery or ophthalmic steroids are permissible).
  - f. Be on an antihypertensive agent or diabetic regimen at a dose that has not been stable for at least 30 days or which is not expected to remain stable while participating in the study.
5. In the opinion of the Investigator, within the past year have a history of illicit drug use or prescription medicine or alcohol abuse (regularly drinks > 4 units of alcohol per day; where a unit = 8 oz. beer, 3 oz. wine or 1 oz. spirits).
6. Have positive results on the alcohol test (breath or saliva) indicative of alcohol abuse or urine drug screen indicative of illicit drug use (unless results can be explained by a current prescription or acceptable over-the-counter medication at screening as determined by the investigator) at screening, and/or prior to surgery.
  - a. Note that for those subjects who test positive for tetrahydrocannabinol (THC), if they are willing to abstain from use or consumption of THC-containing products from 3 days prior to surgery to the day 8 visit, they may be allowed to participate

in the study. Additionally, it may be permissible for the subject to participate if the results can be explained by a current prescription or acceptable over-the-counter medication as determined by the investigator at screening, and/or prior to surgery.

7. Have previously participated in a clinical study with CA-008.
8. Have participated in another clinical trial or used an investigational product within 30 days or five half-lives (whichever is longer) prior to the planned bunionectomy surgery, or is scheduled to receive an investigational product other than CA-008 while participating in the study.

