	
 
3. If a male, unless he has a same sex partner, be either sterile (surgically or biologically) or commit to an acceptable method of birth control while participating in the study. The site personnel will provide instructions on what is an acceptable method.
 
4. If a female of child-bearing potential (FCBP), must meet all of the following:             
 
a. Not be pregnant (FCBP must have a negative serum pregnancy test at screening and negative urine pregnancy test before surgery);
 
b. No plan to become pregnant or to breast feed during the study; and
 
c. Be surgically sterile or at least one year post-menopausal, have a monogamous partner who is surgically sterile, have a same sex partner or (one of the following must apply)                 
 
i. is practicing double-barrier contraception
 
ii. is practicing abstinence (must agree to use double-barrier contraception in the event of sexual activity)
 
iii. is using an insertable, injectable, transdermal or combination oral contraceptive approved by the FDA for at least 2 months prior to screening and commits to the use of an acceptable form of birth control while participating in the study.
 
 
 
 
 
5. Have a body mass index <math>\leq 40</math> kg/m^2.
 
6. Be willing and able to sign the informed consent form (ICF) approved by an Institutional Review Board (IRB).
 
7. Be willing and able to complete study procedures and pain scales and to communicate meaningfully in English with study personnel and return for outpatient follow up visits as required.
 
8. For the portion of subjects who will participate in the PK analyses, be willing to undergo 17 blood draws for PK assessments at various time points during the surgery and the following 24 hours.
 

Exclusion Criteria:
	
If any of the following exclusion criteria apply, subjects may not participate in the study:
 
 
1. In the opinion of the Investigator,
 

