	
 
a. have a concurrent painful condition, other than bunion-related pain, that may require analgesic treatment during the study period or may confound post-surgical pain assessments.
 
b. have active skin disease or other clinically significant abnormality at the anticipated site of surgery that could interfere with the planned surgery.
 
 
2. Have a known allergy to chili peppers, capsaicin or the components of CA-008, bupivacaine HCl, ketorolac, acetaminophen or oxycodone.
 
3. As determined by the investigator (with input from the study's medical monitor if requested by the investigator), have a history or clinical manifestation of significant medical, neuropsychiatric or other condition, including an existing arrhythmia, left bundle branch block, myocardial infarction within the prior 6 months, clinically significant abnormal ECG or clinical laboratory test value, that could preclude or impair study participation or interfere with study assessments.
 
4. The following are considered disallowed medications:
 
 
a. Be tolerant to opioids defined as those who have been receiving or have received chronic opioid therapy greater than 15 mg of oral morphine equivalents (Table 5) per day for greater than 4 out of 7 days per week over a one-month period within 6 months screening.
 
b. Within 1 day prior to surgery and throughout the inpatient period, be taking any capsaicin-containing products, such as dietary supplements or over-the-counter (OTC) preparations, including topical formulations, and prescription medications.
 
c. Within the 7 days prior to surgery, be taking any central nervous system (CNS) active analgesic adjunct medication, such as anticonvulsants, antidepressants (such as SNRIs, SSRIs, and tricyclic antidepressants), benzodiazepines, sedative-hypnotics, clonidine and other central alpha-2 agents (e.g., tizanidine), ketamine or muscle relaxants. [Note that SNRIs = Serotonin and norepinephrine reuptake inhibitors and SSRI = Selective serotonin reuptake inhibitors.] 
 
i. These drugs are permitted if prescribed for non-pain indications and the dose has been stable for at least 30 days prior to surgery. Note that the dose must remain stable throughout the study.
 
ii. If the subject is taking centrally- and/or peripherally-acting analgesic medications, such as acetaminophen, NSAIDs,
 
 
 

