--	---

	
tramadol or opioids, FOR bunion-related pain, the subject may participate in the study if 4(a) above is not applicable and the subject is willing to discontinue these medications 3 days prior to surgery.
 
iii. The use of benzodiazepines and the non-benzodiazepines (eszopiclone, ramelteon, zaleplon and zolpidem) are permitted to treat insomnia during the postoperative period.
 
d. Within the 7 days prior to the planned surgery and throughout the study, be taking antiarrhythmics except beta-blockers, digoxin, warfarin (see exception below), lithium, or aminoglycosides or other antibiotics for an infection (except for ophthalmic use or for treatment or prophylaxis of postoperative surgical site infections). (Use of warfarin or other agents is allowed, at the investigator's discretion, for DVT prophylaxis after the surgery is completed).
 
e. Within the 14 days prior to surgery, be taking parenteral or oral corticosteroids (steroid inhaler for allergy or asthma treatment, topical steroid for a non-clinically significant skin condition not involving the area of surgery or ophthalmic steroids are permissible).
 
f. Be on an antianginal, antihypertensive agent or diabetic regimen at a dose that has not been stable for at least 30 days or which is not expected to remain stable while participating in the study.
 
5. In the opinion of the Investigator, within the past year have a history of illicit drug use or prescription medicine or alcohol abuse (regularly drinks > 4 units of alcohol per day; where a unit = 8 oz. beer, 3 oz. wine or 1 oz. spirits).
 
6. Have positive results on the alcohol test (breath or saliva) indicative of alcohol abuse or urine drug screen indicative of illicit drug use (unless results can be explained by a current prescription or acceptable over-the-counter medication at screening as determined by the investigator) at screening, and/or prior to surgery.
 
a. Note that for those subjects who test positive for tetrahydrocannabinol (THC), if they are willing to abstain from use or consumption of THC-containing products from 3 days prior to surgery to the day 8 visit, they may be allowed to participate in the study. Additionally, it may be permissible for the subject to participate if the results can be explained by a current prescription or acceptable over-the-counter medication as determined by the investigator at screening, and/or prior to surgery.
 
7. Have previously participated in a clinical study with CA-008.

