## **12.2. Eligibility Review and Randomization**

Prior to randomization, subjects must meet all inclusion and not meet any exclusion criteria as outlined in [Section 10.1](#) and [Section 10.2](#).

The Investigator or designee must document that the subjects met each individual criterion via a signed note or eligibility and inclusion/exclusion checklist during Screening and at D0 prior to surgery. Signatures on these documents must be dated on or before the date of randomization on the day of surgery.

Randomization will be accomplished manually.

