## 1. APPENDICES

### APPENDIX A: AMERICAN SOCIETY OF ANESTHESIOLOGISTS PHYSICAL STATUS CLASSIFICATION SYSTEM (ASA CLASS)

I	Normal healthy patient
II	Patient with mild systemic disease; no functional limitation – e.g. smoker with well-controlled hypertension
III	Patient with severe systemic disease; definite functional impairment – e.g. diabetes and angina with relatively stable disease, but requiring therapy
IV	Patient with severe systemic disease that is a constant threat to life – e.g. diabetes and angina and congestive heart failure; patients with dyspnea on mild exertion and chest pain
V	Unstable moribund patient who is not expected to survive 24 hours with or without operation
VI	Brain dead patient whose organs are removed for donation to another
E	Emergency operation of any type, which is added to any of the above six categories, as in ASA II E

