2.2.1 Study Population

The study population will consist of approximately 144 subjects (36 per treatment group) between the ages of 18 and 75 years who are planning to undergo an elective unilateral BUNX and otherwise meet eligibility criteria (as described in the protocol Sections 10.1 and 10.2) may be considered for enrollment into the study.

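### Exclusion criteria 3 and 4f differ between the synopsis and Section 10.2, and two of the three doses in Table 4 are tenfold below the table's own concentration times 14 mL

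*Protocol*

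**What the plan says.** **Exclusion 3.** The synopsis lists examples of significant conditions: "including an existing arrhythmia, left bundle branch block, myocardial infarction within the prior 6 months, clinically significant abnormal ECG or clinical laboratory test value". Section 10.2 has the same criterion with one example: "including a clinically significant abnormal clinical laboratory test value, that could preclude or impair study participation". Both leave the determination to the investigator, with medical monitor input on request.

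**Exclusion 4f.** The synopsis reads "Be on an antianginal, antihypertensive agent or diabetic regimen at a dose that has not been stable". Section 10.2 reads "Be on an antihypertensive agent or diabetic regimen at a dose that has not been stable for at least 30 days". Both add a second limb covering regimens that are not expected to stay stable during the study.

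**Which list applies.** The synopsis introduces its own list with "If any of the following exclusion criteria apply, subjects may not participate in the study". Section 12.2 requires that "subjects must meet all inclusion and not meet any exclusion criteria as outlined in" Sections 10.1 and 10.2. SAP 2.2.1 takes its population from subjects who "otherwise meet eligibility criteria (as described in the protocol Sections 10.1 and 10.2", and SAP 2.2.3 points to the same two sections.

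**Table 4 (Section 11.1.2).** Vials of 2.5, 7.5 and 15 mg, constituted with 49 mL of saline, are shown at 0.05, 0.15 and 0.30 mg/mL. The doses in 14 mL are printed as 0.7, 0.21 and 0.42 mg. The synopsis, Section 9.1.2.2 and SAP 2.2.2 pair the same concentrations and volume with 0.7, 2.1 and 4.2 mg.

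**The concern.** Eligibility needs one list. Where two lists differ, the same subject can be properly enrolled under one and an inclusion/exclusion deviation under the other. SAP 4.3 has a category for such deviations and summarises them for the ITT population. The items that differ are cardiac, so they bear on safety. A screening ECG is required, yet only the synopsis names an abnormal ECG in an exclusion criterion.

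Criterion 4f matters most because it is a stability rule and carries no clause leaving its application to the investigator's opinion. Subjects with treated angina are not ruled out elsewhere: inclusion 1 admits ASA class 3, which Appendix A illustrates with "e.g. diabetes and angina with relatively stable disease, but requiring therapy".

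Table 4 is the protocol's study-treatment table. Its dose row contradicts the labels that define the primary comparison (Section 15.6.1), the other dose comparisons (Section 15.6.3) and the linear trend test (SAP 7.5.2).

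**Working it through.** **1. The criteria side by side**

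| | Synopsis | Section 10.2 |
|---|---|---|
| Criterion 3, named examples | arrhythmia; left bundle branch block; recent myocardial infarction (6 months); abnormal ECG; abnormal laboratory value | abnormal laboratory value |
| Criterion 3, who decides | investigator | investigator |
| Criterion 4f, drug classes | antianginal; antihypertensive; diabetic | antihypertensive; diabetic |
| Criterion 4f, test | 30-day stability, or expected instability | same |

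Criterion 3 has five named examples against one, so four are missing from Section 10.2. Criterion 4f has three drug classes against two, so one is missing.

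Take a subject on an antianginal agent that is not also counted as an antihypertensive, with a dose stable for less than 30 days. Synopsis 4f excludes this subject. Section 10.2 4f does not, and exclusion then rests on the investigator's judgment under criterion 3.

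For a subject with one of the four cardiac conditions, both versions of criterion 3 allow exclusion. Section 10.2 criterion 4d also still restricts antiarrhythmics.

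**2. Table 4**

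Concentration = vial content / (1 mL + 49 mL). Dose = concentration × 14 mL.

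| Vial | Concentration | Concentration × 14 mL | Printed dose | Ratio |
|---|---|---|---|---|
| 2.5 mg | 2.5/50 = 0.05 mg/mL | 0.70 mg | 0.7 mg | 1 |
| 7.5 mg | 7.5/50 = 0.15 mg/mL | 2.10 mg | 0.21 mg | 10 |
| 15 mg | 15/50 = 0.30 mg/mL | 4.20 mg | 0.42 mg | 10 |

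The concentration row reproduces from the vial contents. In the dose row, one entry of three agrees and two are exactly tenfold lower than the product. Concentrations rise 1 : 3 : 6, but printed doses run 1 : 0.3 : 0.6, so the weakest vial carries the largest printed dose.

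**3. Cross-check against the SAP trend contrast**

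SAP 7.5.2 gives coefficients −1.75, −1.05, 0.35 and 2.45.

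- Doses 0, 0.7, 2.1 and 4.2 mg: mean = 7.0/4 = 1.75. Centred values are −1.75, −1.05, 0.35 and 2.45, identical to the SAP.
- Doses as printed in Table 4 (0, 0.7, 0.21 and 0.42 mg): mean = 1.33/4 = 0.3325. Centred values are −0.3325, 0.3675, −0.1225 and 0.0875, which do not match.

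**4. Sample size**

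Section 15.2 uses a difference of −100 and an SD of 130. No dose in mg enters the formula:

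n = 2 × (1.960 + 1.282)² × 130²/100² ≈ 35.5, rounded up to 36 per arm.

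Power at 36 per arm is 0.904 by the normal approximation and 0.896 by the noncentral t. The stated 36 per arm and 90% reproduce and are unaffected.

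**The case against.** **Criterion 3 has the same operative test in both places.** This stands. The four cardiac items sit inside a clause that already depends on investigator judgment, and the body of the protocol still requires a screening ECG and review of its clinical significance. What is lost is explicit prompting.

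**Section 10.2 is the list that governs in practice.** Section 10.4, Section 12.2 and SAP 2.2.1 and 2.2.3 all cite Sections 10.1 and 10.2, and a site could satisfy both lists by applying every exclusion in either. The citations are real, but they do not settle the matter. The synopsis states its exclusions as bars to participation, no precedence rule is given, and the list cited is the shorter one.

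**The reach of 4f is narrow.** Appendix A describes relatively stable disease, inclusion 1 requires a reasonably healthy adult, and 4f names no date from which the 30 days are counted. These points limit how many subjects could be affected, and the documents give no number. They do not remove the difference between the two texts.

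**Table 4 is an obvious misprint without consequence.** Every subject receives 14 mL from blinded, numbered vials, preparation follows the Pharmacy Manual, and the contrast coefficients are fixed numbers in the SAP. It is correct that no misdosing follows from the printed row. The table is nevertheless offered as a clarification of the treatment solutions, and it contradicts itself.

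**No analysis depends on eligibility.** Correct: none of the six SAP populations is defined by the entry criteria. The effect is on enrolment and on deviation reporting.

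**Conclusion.** The point holds: both contradictions are in current text and should be fixed. Four named cardiac examples and one drug class appear in the synopsis list but not in Section 10.2. Criterion 4f is the substantive difference, because one text bars a subject whom the other leaves to judgment. That conclusion assumes the antianginal agent is not also treated as an antihypertensive. In Table 4, two of three doses are tenfold below concentration times volume and conflict with the synopsis, Sections 9.1.2.2, 11.4, 15.6.1 and 15.6.3, SAP 2.2.2 and the SAP 7.5.2 contrast.

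The documents show no misdosing, and neither the sample size nor the primary analysis changes. The Pharmacy Manual and the eligibility checklist are not part of the documents, so whether either carries the same conflict is unknown. No view is taken here on which criterion or dose is right.

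**What to change.** - The sponsor's medical team reconciles criteria 3 and 4f in the synopsis and Section 10.2 into one list.
- That list is used for the eligibility checklist required by Section 12.2 and for coding inclusion/exclusion deviations under SAP 4.3. The checklist in use should be compared with it.
- The Table 4 dose row is reconciled with its concentration row, Section 9.1.2.2, SAP 2.2.2 and the SAP 7.5.2 contrast.

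The cost is one protocol amendment. Section 16.6 requires IRB approval before implementation, except for changes that remove an immediate hazard or are logistical or administrative. The criteria change may therefore need prior approval, while the table change may qualify as administrative. Neither change calls for new data collection or a change to the sample size.
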